6.3.3 Unanticipated Problem (UP)

Unanticipated problems include any incident, experience, or outcome that meets all of the following criteria:

- Unexpected (in terms of nature, severity, frequency) given (a) the
 research procedures that are described in the protocol-related
 documents, such as the IRB-approved research protocol and informed
 consent document; and (b) the characteristics of the subject population
 being studied;
- Related or possibly related to participation in the research (possibly related means there is a reasonable possibility that the incident, experience, or outcome may have been caused by the procedures involved in the research); and
- Suggests that the research places subjects or others at a greater risk of harm (including physical, psychological, economic, or social harm) than was previously known to an individual or group of individuals (including research subjects, research staff, or others not directly involved in the research).

6.3.4 Evaluable for toxicity

Any patient who receives at least one dose of study drug is evaluable for toxicity and will be included in the safety analysis.

6.4 Severity of Adverse Events

All non-hematologic adverse events will be graded according to the NCI Common

Terminology Criteria for Adverse Events (CTCAE) version 5.0. The CTCAE v5 is available at http://ctep.cancer.gov/reporting/ctc.html.

If no CTCAE grading is available, the severity of an AE is graded as follows:

Mild (grade 1): the event causes discomfort without disruption of normal daily activities.

Moderate (grade 2): the event causes discomfort that affects normal daily activities.

Severe (grade 3): the event makes the patient unable to perform normal daily activities or significantly affects his/her clinical status.

Life-threatening (grade 4): the patient was at risk of death at the time of the event.

Fatal (grade 5): the event caused death.

6.5 Reporting Requirements for Adverse Events

6.6 Steps to Determine If an Adverse Event Requires Expedited Reporting

- Step 1: Identify the type of adverse event using the NCI Common Terminology Criteria for Adverse Events (CTCAE v5).
- Step 2: Grade the adverse event using the NCI CTCAE v5.

Step 3: Determine whether the adverse event is related to the protocol therapy Attribution categories are as follows:

- Definite The AE is clearly related to the study treatment.
- Probable The AE is likely related to the study treatment.
- Possible The AE *may be related* to the study treatment.
- Unrelated The AE is clearly NOT related to the study treatment.

Note: This includes all events that occur within 30 days of the last dose of protocol-defined treatment. Any event that occurs more than 30 days after the last dose of protocol-defined treatment and is attributed (possibly, probably, or definitely) to the agent(s) must also be reported accordingly.

Step 4: Determine the prior experience of the adverse event.

Expected events are those that have been previously identified as resulting from administration of the agent. An adverse event is considered unexpected when either the type of event or the severity of the event is not listed in the current known adverse events listed in the package insert.

6.6.1 Expedited Reporting

6.6.1.1 Reporting to the Principal Investigator

The Principal Investigator must be notified within 24 hours of learning of any serious adverse events, regardless of attribution, occurring during the study or within 30 days of the last protocol-defined administration of the study drug.

PI Phone Number for Expedited Reporting: [name] [contact]

Alternate Phone Number for Expedited Reporting: [name] [contact]

6.6.1.2 Reporting to the DSMC

Serious Adverse Events deemed to be related to the protocol and on-study deaths, including death of a research subject unless the death is expected (e.g. due to disease progression) to be reported to the DSMC within 24 hours of awareness for medical monitor ad hoc review between meetings to determine if immediate action is required. Reports to be emailed to the DSMC team at [contact].

6.6.1.3 Reporting to the Institutional Review Board (IRB)

The IRB must be notified within 10 business days of "any unanticipated problems involving risk to subjects or others."

- 1. Any serious event (injuries, side effects, deaths or other problems), which in the opinion of the Principal Investigator was unanticipated, involved risk to subjects or others, and was possibly related to the research procedures.
- 2. Any serious accidental or unintentional change to the IRB-approved protocol that alters the level of risk.
- 3. Any deviation from the protocol taken without prior IRB review to eliminate apparent immediate hazard to a research subject.
- 4. Any new information (e.g., publication, safety monitoring report, updated sponsor safety report), interim result or other finding that indicates an unexpected change to the risk/benefit ratio for the research.
- 5. Any breach in confidentiality that may involve risk to the subject or others.
- 6. Any complaint of a subject that indicates an unanticipated risk or that cannot be resolved by the Principal Investigator.

6.6.1.4 Reporting to the External Funding Source (Vivus)

All SAEs to be forwarded to Vivus within 24 hours of awareness. This will allow Vivus to cross report to other clinical trials/investigators in a timely manner. Vivus may request additional or supportive information to clarify details in a follow-up report and will submit request to the site in writing.

Reports should be submitted to: [contact]

7.0 CORRELATIVES/SPECIAL STUDIES

7.1 Research Blood Collection Kit and Instructions

Patients will be instructed to fast for at least 8 hours prior to research blood draws and blood draws must be scheduled in the morning. Deviations from this must be recorded. This Kit is for collection, processing, storage and/or shipping of serum, plasma, or whole blood (as specified by the protocol):

Kit contents:

• One (1) 5 – 10 cc Red Top tube for serum (A)

- One (1) 5 10 cc Lavender Top EDTA preserved with anticoagulant tube for plasma (B)
- One (1) 5 10 cc Lavender Top EDTA preserved with anticoagulant tube for Whole Blood (C)
- Fifteen (15) to thirty (30) 1 ml cryovials
- Pipettes
- Two (2) patient-specific cryovial storage boxes
- Biohazard bags (3) and Absorbent shipping material (3)
- Styrofoam container (inner) and Cardboard shipping (outer) box
- UN1845 DRY Ice Sticker and UN3373 Biological Substance Category B Stickers
- Lab Requisition Form and Kit Instructions

7.1.1 Preparation and processing of serum, plasma, and whole blood

7.1.2 Serum: Red Top Tube

- Label as many 1ml cryovials (up to 5-10) as necessary for the serum collected.
 Label them with:
 - Study name: PanCax3
 - Subject ID
 - Patient initials (First, Middle, Last)
 - Collection date (Month, Day, Year)
 - Serum cryovial number (e.g., S1, S2, S3, S4, S5, etc...)

7.1.2.1 **Process**

[figure not shown]
- Transport Red Top Tube for processing at room temperature
- Allow the blood to clot by leaving it undisturbed at room temperature (15-30 minutes)
- Centrifuge at 1,000 x g for 10 minutes in a refrigerated centrifuge (4°C). If unable to process samples at 4°C then spinning at room temperature is acceptable if done within 2 hours of draw but must be noted on the Lab Requisition Form.
- Aliquot 0.5 ml serum into as many 1 ml cryovials (up to 5-10) as are necessary for the serum collected and stored at -80°C. Ensure the patient initials, collection date and serum cryovial number (e.g., S1, S2, S3, S4, S5, etc...) are marked on the cryovials.
- Place cryovials into the patient-specific cryovial storage box and immediately freeze at -70 to -90° C, and store frozen until ready to ship/transfer. See below for storage conditions.

7.1.3 Plasma: Lavender Top EDTA tube #1

- Label as many 1ml cryovials (up to 5-10) as necessary for the plasma collected. Label them with:
 - Study name: PanCax3
 - Subject ID
 - Patient initials (First, Middle, Last)
 - Collection date (Month, Day, Year)
 - Plasma cryovial number (e.g., P1, P2, P3, P4, P5, etc...)

7.1.3.1 **Process**

- After collection, invert tube(s) twice to ensure adequate mixing of EDTA.
- Centrifuge specimen(s) within one hour of collection at 2,000 x g for 15 minutes in a refrigerated centrifuge (4°C). If unable to process samples at 4°C then spinning at room temperature is acceptable if done within 2 hours of draw but must be noted on the Lab Requisition Form.
- If the interval between specimen collection and processing is anticipated to be more than one hour, keep specimen on ice until centrifuging is performed.
- Aliquot 0.5 ml plasma into as many 1 ml cryovials (up to 5-10) as are necessary for the plasma collected and stored at -80°C. Ensure the patient initials, collection date and plasma cryovial number (e.g., P1, P2, P3, P4, P5, etc...) are marked on the cryovials.
- Place cryovials into the patient-specific cryovial storage box and immediately freeze at -70 to -90° C, and store frozen until ready to ship/transfer. See below for storage conditions.

7.1.4 Whole Blood: Lavender Top EDTA tub #2

Label as many 1ml cryovials (up to 5-10) as necessary for the whole blood collected. Label them with:

- Study name: PanCax3
- Subject ID
- Patient initials (First, Middle, Last)
- Collection date (Month, Day, Year)
- Whole blood cryovial number (e.g., WB1, WB2, WB3, WB4, WB5, etc...)

7.1.4.1 Process

- After collection, invert tube(s) twice to ensure adequate mixing of EDTA.
- Blood can also be mixed for 5 minutes on a mixer at room temperature.
- Aliquot 0.5 ml blood into as many 1 ml cryovials (up to 5-10) as are necessary for the whole blood collected and stored at -80°C. Ensure the

patient initials, collection date and whole blood cryovial number (e.g., WB1, WB2, WB3, WB4, WB5, etc...) are marked on the cryovials.

 Place cryovials into biohazard bag and immediately freeze at -70 to -90° C, and store frozen until ready to ship/transfer. See below for storage conditions.

7.1.5 All Blood Samples - Freezing and Storage

- Freeze all blood samples in a -80°C Freezer or on Dry Ice or snap freeze in liquid nitrogen.
- Store at -80°C (-70°C to -90°C) until ready to transfer.
- If a -80°C Freezer is not available,
- Samples can be stored short term in a -20°C freezer (non-frost free preferred) for up to one week; OR
- Samples can be stored in plenty of dry ice for up to one week, replenishing daily; OR
- Samples can be stored in liquid nitrogen vapor phase
- Please indicate on Lab Requisition the storage conditions used and time stored.

8.0 FECAL SPECIMEN COLLECTION

8.1 Materials

- Toilet hat
- Collection bucket
- Gloves
- Sterile container with scooper attached to cap
- Biohazard laboratory bags (2)
- Post-it to record collection date and time
- Styrofoam ice box
- Ice packs

8.2 Home Instructions (see Appendix H)

8.3 Storage of stool sample

The sample should be frozen until transport to the visit. The specimen should be transported frozen and kept frozen upon delivering specimen. Upon receipt of the sample at the investigator site – site personnel should verify that the collection date and subject ID is written on the paper. Stool specimens will be submitted to the CCTO laboratory for documentation and temporary storage in -20°C or -80°C.

9.0 STATISTICAL CONSIDERATIONS

9.1 Power Assessment

The primary hypothesis to be tested is whether the percentage of patients who complete the course of pancreatic enzyme replacement therapy at 8 weeks is at least 50% for each of the three cancer stage subgroups: borderline resectable, locally advanced and advanced pancreatic cancer. We assumed a sample size equal to 10 patients for each group. The minimum detectable difference from the proportion 0.5 is 0.417 using a Binomial Exact test with Bonferroni correction. Thus, we will declare the sustainability of the therapy if 9 or more patients complete the treatment for each subgroup.

9.2 Data Analysis Plan

The primary hypothesis to be tested is whether is the percentage of patients who complete the pancreatic enzyme replacement therapy at 8 weeks is at least 50% for each of the three cancer stage subgroups: borderline resectable, locally advanced and advanced pancreatic cancer. A 95% confidence interval [1] for the proportion of treatment completeness will be calculated for each cancer stage. The statistical analysis will be performed in three steps for all secondary endpoints: 1) Descriptive analysis: Measures of central tendency (mean, median and mode), measures of variability (standard deviation, range and quantiles). Standard distribution plots such as profiles-plots for repeated measures and box-plots will be constructed to examine the distribution of the data. 2) Univariable Analysis and 3) Multivariable analysis: The linear regression model will be applied to explain the secondary endpoints as a function of the patient's baseline variables. Assumptions of the linear regression model will be examined. If the assumptions are not met. Generalized Additive models for Location, Scale and Shape (GAMLSS) which provide a general framework for extending a standard linear model will be applied [2]. The goodness of fit for each model will be accessed through a residual analysis using Worm-plots [51] and variable selection will be performed as outlined by Harrell [4]. Random effects will be added to describe the repeated measures. In addition, overall survival curve will be estimated using the Kaplan-Meier method with 95% confidence interval. All tests of hypotheses will be two-sided and a significance level of 0.05 and calculations will be performed using R, version 3.2.3 [5].

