EOT End-of-Treatment FΑ Folinic Acid (Leucovorin) GLP-1 Glucagon-like peptide-1 H&P History & Physical Exam

HRPP Human Research Protections Program

IL1a Interleukin 1-alpha IV (or iv) Intravenously

MTD Maximum Tolerated Dose **LMF** Lipid Mobilizing Factors

LBM Lean Body Mass

NCI National Cancer Institute ORR Overall Response Rate

OS Overall Survival

PAWL Pancreatic Cancer-Associated Weight Loss

[figure not shown]
PBMCs Peripheral Blood Mononuclear Cells

PD Progression of Disease PFS Progression Free Survival

PR Partial Response

PYY Peptide YY

STUDY SCHEMA

Screening Phase

- 1. Informed consent
- 2. Screening
- 3. Eligibility review
- 4. Measure stool fecal elastase
- Measure fatsoluble vitamins

Treatment Phase

Cycle = 28 days

- 1. Measure weight stability
- 2. Assess 24-hour caloric intake
- 3. Assess stool frequency and consistency
- 4. Evaluate microbiome
- 5. Assess activity levels
- 6. Measure quality of life
- 7. Assess inflammatory biomarkers
- 8. Assess the presence of frailty phenotype
- 9. Assess body composition

End-of-Treatment

After C6D28:

- 1. Return pill bottles
- 2. Transition to Soc enzymes

Follow-up Phase

Safety evaluation

Measure fat-soluble vitamins

Survival

Optional sub-study: Followup activity tracking

STUDY SUMMARY

Title	Pancreatic-enzyme replacement therapy with pancreaze (pancrelipase) delayed-release in addition to standard of care for borderline resectable, locally advanced and advanced pancreatic adenocarcinoma patients (PANCAX-3) with cachexia and exocrine pancreatic insufficiency.		
Short Title	PANCAX-3		
Protocol Number	IIT2018-29-[name]-PNCX3		
Phase	Phase 2		
Methodology	Single arm, Single center		
Accrual Duration	18 months		
Study Duration	Approximately 6 months from screening to end of treatment assessment. Subjects will continue to be followed for survival for 36 months.		
Study Center(s)	Single-center, Cedars-Sinai Medical Center		
Objectives	 Feasibility to complete pancreatic enzyme replacement therapy at 8 weeks Measure weight stability at baseline and day 1 of every cycle for 6 months 24-hour caloric intake at baseline, C3D1, and end-of-study Stool frequency at baseline and C3D1 Quality of life assessment baseline and day 1 of every other cycle for 6 months Fitness tracking will be assessed with a wrist-worn wearable activity monitor (e.g., Fitbit Charge HR) continuously from day 1 of cycle 1 until the end of study visit. 		
Number of Subjects	Up to 40 patients (30 evaluable patients)		

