One study randomized patients with pancreatic cancer to either 6 capsules of a high-dose pancreatic enzyme supplement per day or placebo for 8 weeks, with both groups receiving dietary counseling. Patients taking PERT gained 1.2% of their body weight compared with a 3.7% weight loss in the placebo group, with a mean difference in percentage of body weight change of 4.9% (P =.02; 95% confidence interval [CI] for the difference, 0.9%-8.9%). In addition, the fat absorption coefficient improved by 12% among those treated with PERT, while declining 8% for patients taking placebo (P =.13)[33].

Patients with borderline resectable, locally advanced, and advanced disease have distinct treatment paradigms and clinical outcomes. It is known that malabsorption is present in 68-92% of patients at diagnosis and most patients have associated symptoms [3, 6, 35, 38, 39]. In patients who had surgical resections, PERT was shown to improve the digestion of fat and associated symptoms of malabsorption [40]. As the cancer advances and the disease has spread to more area within the pancreas, the reliance on PERT is often increasingly recommended as the pancreas becomes less able to perform normal functions to aid in digestion of food. Previous studies have shown that lower trypsin, lipase and bicarbonate secretion are present in patients with non-resectable pancreatic cancer and pancreatic ductal obstruction [7]. As the utility of PERT varies with respect to each of the three cohorts of patients, it will be important to understand if there are some patient cohorts with an increased need for PERT.

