2.4.3 Exploratory Hypotheses

- Improve quality of life and symptoms of pain from baseline
- Patient-reported response the therapy will improve

- Fecal elastase may correlate with response to pancreatic enzyme supplementation
- Survival and response rate may benefit from a comprehensive approach to nutritional support
- Pancreatic enzyme supplementation will be safe and tolerable
- Weight loss and cachexia may be associated with genomic and stromal alterations in the tumor.
- · Inflammatory biomarkers may be improved
- The frailty phenotype may be improved
- Lean body mass may be maintained throughout treatment course

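### Section 9.2 lets variable selection remove stage cohort from the multivariable secondary models and plans one unstratified survival curve, although stage structures the primary endpoint and the rationale asks about it

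*Combined protocol and SAP*

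**What the plan says.** Section 9.2 sets out three steps for all secondary endpoints: descriptive, univariable and multivariable. The model is a linear regression, or GAMLSS if its assumptions fail, "to explain the secondary endpoints as a function of the patient's baseline variables". Random effects are added for repeated measures. The baseline variables are not listed. Variable selection follows, credited to reference [4], with no term kept by design and no retention threshold. Entry 4 in the Section 11 list is a study of cachexia and prognosis in resectable pancreatic cancer, so the rule cannot be traced.

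On survival, the same section says only that the "overall survival curve will be estimated using the Kaplan-Meier method with 95% confidence interval". It names no strata. For the primary endpoint, by contrast, it asks for a confidence interval for each stage, and Sections 2.5.1 and 9.1 apply the success criterion cohort by cohort.

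Section 1.3 states that the three stages are managed differently and have different outcomes, and that "it will be important to understand if there are some patient cohorts with an increased need for PERT". Section 2.4.3 adds an exploratory hypothesis: "Fecal elastase may correlate with response to pancreatic enzyme supplementation". Section 9.2 describes no analysis of fecal elastase, and response is not defined.

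**The concern.** The protocol gives a reason to look at stage and builds its primary endpoint on stage. For the secondary endpoints, such as weight, caloric intake, stool measures, vitamins and activity, it leaves the role of stage to a data-driven step.

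With about 30 patients, that step is a poor way to settle the matter. If stage is dropped, the multivariable model reports no stage estimate, and its absence may be read as evidence that stage does not matter. If a term is kept because it passed a threshold, its coefficient tends to be too large. Either way, the reader lacks the useful result: an estimate for each stage with an interval that shows how imprecise it is.

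Survival raises a similar issue. If the curve is pooled, as the wording suggests, it partly reflects how many patients of each stage enrolled.

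**Working it through.** **1. The plan's own figure.** Section 9.1 gives the only computed figure, and it concerns the primary endpoint: "We assumed a sample size equal to 10 patients for each group", and "The minimum detectable difference from the proportion 0.5 is 0.417 using a Binomial Exact test with Bonferroni correction". The rule is success "if 9 or more patients complete the treatment for each subgroup".
- P(X≥9 | n=10, p=0.5) = (10+1)/1,024 = 0.0107, below 0.05/3 = 0.0167 (one-sided).
- Power at p=0.917 is 0.801, and 80% power is reached at p=0.9167, a difference of 0.417. The figure reproduces with an assumed 80% power, which the plan does not state.

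Nothing comparable exists for the secondary models or survival, so the remaining steps rest on assumptions.

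**2. Inputs.** From the documents: 30 evaluable patients (up to 40 enrolled), 10 per stage, significance level 0.05. Assumed: effect size f² = 0.15 (medium) or 0.35 (large) for both stage and elastase; 4 or 8 irrelevant candidate variables; backward elimination by p<0.05 or by AIC; one outcome per patient.

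In the simulation the stage means are −d, 0 and +d residual SDs with d = √(1.5 f²).
- f² = 0.15: d = √0.225 = 0.47, so the extreme stages differ by about 0.95 SD.
- f² = 0.35: d = √0.525 = 0.72, so they differ by about 1.45 SD.

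**3. Analytic check.** In a four-parameter model (intercept, 2 df for stage, 1 df for elastase) the noncentrality is λ = f²N. At N=30 and f²=0.15, λ = 0.15×30 = 4.5 with 26 residual df.
- Probability that the term misses p<0.05: stage 0.58, elastase 0.47.
- At f²=0.35: 0.21 and 0.12.
- At f²=0.02: 0.91 and 0.88.

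**4. Simulated selection, N=30.** 2,000 runs per setting; ranges cover 4 and 8 irrelevant candidates.

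| Assumed effect | Rule | Stage dropped | Elastase dropped | At least one | Both |
|---|---|---|---|---|---|
| f²=0.15 | p<0.05 | 56–57% | 51–52% | 78–79% | 29–30% |
| f²=0.15 | AIC | 29–31% | 27% | 47–48% | 8–9% |
| f²=0.35 | p<0.05 | 23–25% | 20% | 37–38% | 5–6% |
| f²=0.35 | AIC | 7–8% | 7–10% | 14–16% | 1% |

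Monte Carlo error near 78% is about 1.96×√(0.78×0.22/2,000) = 0.018. With 39 patients, at least one term is dropped in 66–67% (p<0.05) or 37–40% (AIC) at f²=0.15, and in 20% or 7% at f²=0.35.

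**5. Size of retained estimates.** When elastase survives selection at N=30 and f²=0.15, its mean coefficient is about 1.4 times the true value under p<0.05 and about 1.2 times under AIC.

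**6. Size of a fixed model.** Stage (2 df) plus the endpoint's baseline value (1 df) uses 3 df besides the intercept: 30/3 = 10 patients per df. The chance of losing stage is then zero by construction.

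**7. Precision of survival by stage.** Without censoring, the half-width is 1.96×√(S(1−S)/n). At S=0.5 this is 1.96×√(0.25/10) = 0.31 for one stage and 1.96×√(0.25/30) = 0.18 pooled.

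**The case against.** The case for leaving the plan alone has real force.

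- **The rule is unknown.** Section 9.2 refers to a published approach, and the documents do not show what it is. It may not be stepwise elimination. This stands: the rates above are illustrations, and they vary about fivefold across the settings at N=30 (14% to 79%).
- **Dropping is permitted, not planned.** A reader might infer that stage and elastase will go unreported. The text does not say so. The univariable step is not described as a screen, and both could be reported there. Neither is named there, however.
- **Low power is not the harm.** A reader might take the F-test power for stage (0.458 for means of 0, 0.5 and 1 SD, 10 per cohort) as the damage done by selection. Forcing stage into the same model does not raise that power. It only ensures that the estimate and interval are reported.
- **The stated questions are modest.** No objective or hypothesis in Sections 2.1 to 2.4 calls for comparing secondary endpoints between stages; that question sits in the rationale. Elastase and survival are exploratory.
- **The survival mix.** A reader might infer that the pooled curve describes an artificial mix fixed at 10/10/10 and therefore no real population. Section 9.1 assumes 10 per group, but no quota or cap is stated and Section 1.1 speaks of consecutive patients. Pooling itself is inferred from the singular wording and the absence of strata.
- **Elastase data are imperfect.** Eligibility rests on a clinical diagnosis (Section 3.1.4), and Section 5.2 allows the sample up to seven days after C1D1. Requiring elastase in every model could lose patients or use values taken on treatment.

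The elastase objection changes the remedy: elastase belongs in a separate analysis. The others limit the size of the point. They do not answer why stage is unprotected in the secondary models.

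**Conclusion.** The point holds as a weakness of the secondary and exploratory analyses. Section 9.2 chooses a method, selection among unlisted variables with none retained by design, under which stage may vanish from the multivariable models. It does not provide for survival by stage. A better method is available at the cost of wording.

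The size is uncertain. At 30 patients, stage or elastase is dropped in about 47% to 79% of runs under assumed medium effects and about 14% to 38% under large ones. The lower figure in each pair is for AIC and the upper for p<0.05. These rates assume independent candidate variables, equal effects for the two terms and a single outcome per patient; the planned repeated measures would change them. The documents do not support the claim that selection will discard real stage differences at any particular rate. The primary analysis keeps stage throughout and is unaffected.

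**What to change.** In Section 9.2:

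1. Prespecify the secondary model with stage cohort (three levels) and, where one exists, the endpoint's baseline value, both retained regardless of p-value. Activity monitoring starts on day 1 of cycle 1, so that endpoint may have no pre-treatment value.
2. List the other candidate variables, correct the citation for the selection method, and label any model with selected covariates as exploratory.
3. Report secondary changes and Kaplan-Meier survival by stage with 95% intervals, descriptively, beside the pooled results.
4. For Section 2.4.3, add a separate exploratory analysis: the association of continuous fecal elastase with a prespecified response, such as weight change, with a 95% interval, in patients who have a sample. Add a sensitivity analysis restricted to samples taken before treatment.

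The cost is wording, with no new data. By-stage intervals will be wide, and the elastase analysis may include fewer patients, especially in the sensitivity analysis.

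### Sections 9.1 and 9.2 do not specify the same primary test: with 9.1's Bonferroni correction and 9.2's two-sided rule both applied, the stated cut-off of 9 of 10 fails

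*Combined protocol and SAP*

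**What the plan says.** Section 9.1 (Power Assessment) tests the completion proportion at 8 weeks "for each of the three cancer stage subgroups: borderline resectable, locally advanced and advanced pancreatic cancer". On size it says "We assumed a sample size equal to 10 patients for each group". On the test it says "The minimum detectable difference from the proportion 0.5 is 0.417 using a Binomial Exact test with Bonferroni correction". The decision rule follows: "we will declare the sustainability of the therapy if 9 or more patients complete the treatment for each subgroup". The section gives no significance level, sidedness or power, and it leaves the Bonferroni divisor to be inferred from the three cohorts.

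Section 9.2 (Data Analysis Plan) restates the primary hypothesis and then plans the estimate: "A 95% confidence interval [1] for the proportion of treatment completeness will be calculated for each cancer stage". It ends with the only statement of alpha and sidedness in the document: "All tests of hypotheses will be two-sided and a significance level of 0.05". That sentence does not exempt the primary test, and 9.2 does not repeat the correction.

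**The concern.** Because 9.1 names a correction but no alpha, and 9.2 names an alpha and a sidedness but no correction, the natural reading combines them: a two-sided exact test at 0.05/3 in each cohort. The cut-off of 9 and the difference of 0.417 do not come from that test.

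The disagreement falls on the very result that 9.1 names as just sufficient. An analyst who applies the count rule declares success in a cohort with 9 of 10. An analyst who applies 9.1's correction to 9.2's two-sided test does not. If this is left open, the choice between them is made with the data in hand, on the primary hypothesis.

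**Working it through.** **Inputs.** From 9.1: p0 = 0.5, n = 10 per cohort, three cohorts, exact binomial test with Bonferroni correction, difference 0.417 (so p1 = 0.917), cut-off 9. From 9.2: alpha 0.05, two-sided, 95% interval. Assumed: divisor 3 (implied by three cohorts); power 80%, with 90% shown as an alternative; exact (Clopper-Pearson) intervals, since the text of 9.2 does not name a method.

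**1. Reproduce 0.417.** With cut-off 9, power at p1 is P(X ≥ 9) = 10·p1⁹·(1 − p1) + p1¹⁰.
- Setting this to 0.80 gives p1 = 0.9167, a difference of 0.417, as stated. At p1 = 0.917 the power is 0.381 + 0.420 = 0.801.
- Setting it to 0.90 gives a difference of 0.445, so 80% is the value that fits.

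**2. Level per cohort.** 0.05/3 = 0.0167, or 0.00833 per tail if two-sided.

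**3. Exact p-values against 0.5.** At p0 = 0.5 the distribution is symmetric, so the two-sided value is twice the upper tail.

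| Result | One-sided p | Two-sided p |
|---|---|---|
| 8 of 10 | 56/1024 = 0.0547 | 0.1094 |
| 9 of 10 | 11/1024 = 0.0107 | 0.0215 |
| 10 of 10 | 1/1024 = 0.00098 | 0.00195 |

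**4. Cut-off under each reading.**

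| Test | Level | Cut-off | Agrees with |
|---|---|---|---|
| One-sided, corrected | 0.0167 | 9 | 9.1, but not 9.2 on sidedness |
| Two-sided, corrected | 0.0167 | 10 | both stated test features, but not 9.1's own figures |
| Two-sided, uncorrected | 0.05 | 9 | 9.2, but not 9.1's correction |

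A one-sided uncorrected test at 0.05 also has cut-off 9 (0.0547 fails, 0.0107 passes), but it contradicts both sections.

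**5. Detectable difference for the two-sided corrected test.** With cut-off 10, power is p1¹⁰.
- 80% power: p1 = 0.8^(1/10) = 0.978, difference 0.478.
- 90% power: p1 = 0.9^(1/10) = 0.990, difference 0.490.
- Power at p1 = 0.917: 0.917¹⁰ = 0.420, against 0.801 with cut-off 9.

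**6. Intervals for 9 of 10.** The planned 95% interval is 0.555 to 0.997 and excludes 0.5. An interval matched to the two-sided corrected test (98.33%) is 0.485 to 0.999 and includes 0.5. The one-sided 98.33% lower bound is 0.528 and excludes 0.5.

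**7. False success under the 9-of-10 rule.** At p = 0.5 a cohort reaches 9 or more with probability 0.0107. The chance that at least one of three does so is 1 − (1 − 0.01074)³ = 0.032.

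**The case against.** The best defence is that 9.1 gives an explicit count rule for a directional hypothesis, so the decision can be made without a p-value, and that the two-sided sentence is a general closing line after the text on secondary endpoints and survival. On that view, 9.1 is internally correct for a one-sided corrected test and has only left the word out. This is fair, and it is the reason the simplest repair keeps the cut-off. It does not remove the conflict: 9.2 covers all tests without exception and opens by restating the primary hypothesis as one to be tested.

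Three stronger readings are tempting and are not supported.

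- A reader might infer that 9.2 by itself rejects 9 of 10. It does not. Section 9.2 contains no correction; 0.0215 is below 0.05, and its planned 95% interval excludes 0.5, in agreement with the count rule. The failure appears only when 9.1's correction is joined to 9.2's sidedness. The 98.33% two-sided interval is likewise not one the plan proposes.
- A reader might infer that the rule inflates the family-wise error to 1 − (1 − 0.0215)³ = 6.3%. That counts results of 0 or 1 of 10, which can never trigger a claim of success. The relevant figure is 3.2% if cohorts are judged separately. If all three must succeed, it is at most 1.07%, reached when two cohorts are certain to pass.
- A reader might take 80% power as the plan's own figure. It is an inference, though a good one, because it returns 0.417.

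**Conclusion.** The point holds as an inconsistency in the specification of the primary test. Taking the correction from 9.1 and the sidedness and alpha from 9.2, the cut-off is 10 of 10, and the detectable difference is 0.478 instead of 0.417 (at 80% power; 0.490 instead of 0.445 at 90%). The stated 9 of 10 and 0.417 require that one section give way: 9.2 on sidedness, or 9.1 on the correction.

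The decision changes only for a cohort with exactly 9 of 10. That is not a remote case: at p1 = 0.917 its probability is 0.801 − 0.420 = 0.381 in each cohort.

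The conclusion rests on a divisor of 3. The two-sided p of 0.0215 passes 0.05/2 = 0.025 and fails 0.05/3. It does not depend on the assumed power, which affects only the detectable difference.

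**What to change.** State sidedness, per-cohort level, power and interval together.

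- In 9.1, say that each cohort is tested with a one-sided exact binomial test of p ≤ 0.5 at 0.05/3, and give the power assumed (80% reproduces 0.417). Then 9 of 10 and 0.417 stand.
- In 9.2, repeat that specification for the primary tests and limit the two-sided 0.05 rule to all other tests. Report the one-sided 98.33% exact lower bound (0.528 for 9 of 10) beside the 95% interval, and label the latter descriptive.
- If a two-sided corrected test is intended, restate the cut-off as 10 of 10 and the difference as 0.478 at 80% power.

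The cost is a few sentences; if the one-sided form is chosen, sample size, conduct and cut-off do not change. It should be settled before the primary data are analysed.

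This does not resolve a separate conflict. Section 2.5.1 counts the primary endpoint as met when at least half the subjects in each cohort are compliant, which is 5 of 10, while 9.1 asks for 9. Those two thresholds must also be reconciled.
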